2.0 INTRODUCTION

2.1 Background

Psoriasis is a chronic inflammatory skin disorder and affects approximately 1% to 2% of people worldwide, with approximately 25% of subjects suffering from moderate to severe chronic plaque psoriasis. Plaque psoriasis, the most common form, affects 80% to 90% of patients. Nail psoriasis occurs in approximately 50% of patients with plaque psoriasis and is associated with pain and discomfort, causing a significant burden to quality of life (QoL) and work function (1). Nail psoriasis affects the nail matrix and the nail bed. The clinical manifestations of psoriasis of the nail matrix include pitting (most common lesion), nail plate crumbling, and leukonychia, while clinical manifestations of psoriasis of the nail bed include the presence of oil-drop or salmon patch dyschromia, onycholysis, subungual hyperkeratosis and splinter hemorrhages (2). Treatment includes topical agents, phototherapy, and/or systemic agents (conventional agents and biological treatments) (3, 4).

2.2 Study Rationale

Biological therapies are indicated for the treatment of subjects with moderate to severe chronic plaque psoriasis who are candidates for phototherapy or systemic therapy. Currently approved biological treatments for moderate to severe plaque psoriasis include tumor necrosis factor (TNF) antagonist agents, i.e., etanercept (Enbrel®), infliximab (Remicade®), and adalimumab (Humira®), and the p40 (IL-12 and IL-23) antagonist ustekinumab (Stelara®). Despite the availability of treatment options for plaque psoriasis, nail lesions remain difficult to treat. The use of topical therapy, typically the first line of treatment for plaque psoriasis, is often challenging because of the poor diffusion into the nail tissue (1, 5). Patient satisfaction and compliance with topical therapy are known to be low (6). Thus, there remains an unmet need for effective therapeutic options for nail psoriasis.

In recent years, accumulating data have implicated the IL-23/Th17 pathway in psoriasis pathogenesis. Recent genome-wide association studies have identified psoriasis risk alleles around gene regions that encode IL-23 (IL23A, IL12B) and the IL-23 receptor (IL-23R) (7, 8). Both p19 and p40 sub-units of IL-23 are over-expressed in psoriatic skin lesions, while the unique p35 sub-unit of IL-12 is not (9). Th17 cells, and the cytokines they elaborate, are abundant in psoriasis lesions, where they exert pro-inflammatory and pro-acanthotic effects (10, 11). Compelling evidence for the functional role of IL-23p19 in psoriasis is demonstrated by a xenotransplant mouse model of psoriasis using AGR-129 mice wherein the administration of anti-human IL-23p19 inhibited the development of psoriatic lesions comparable to anti-TNF-α blockers, the current benchmark in psoriasis treatment (12). It has been shown that disease improvement with anti-TNF-α therapy correlated with the rapid down-modulation of IL-23 and Th17 cell products, and successful response to treatment was dependent on the inactivation of the IL-23/Th17 pathway (13, 14). Thus, while the use of IL-12/IL-23 p40 antagonists (e.g., ustekinumab and briakinumab) have been clinically validated in psoriasis (15-18), recent data suggest that the efficacy of these antagonists likely depends primarily, if not exclusively, on their

ability to neutralize IL-23 rather than IL-12 (8, 19, 20). This provides the rationale for selectively targeting IL-23p19 in subjects with nail psoriasis.

Tildrakizumab is a high affinity (297 pM), humanized IgG1/K antibody that specifically binds to IL-23p19 (SN 08197) but does not bind human IL-12 (IL-12p40 and p35 heterodimer) or human p40. Tildrakizumab 100 mg by subcutaneous (SC) injection has recently been approved by the Food and Drug Administration for the treatment of moderate to severe chronic plaque psoriasis. Detailed information regarding the safety/tolerability of tildrakizumab can be found in the Investigator's Brochure (IB) (21).

Some special populations of patients will not be included in this study, such as those with hepatic, renal, and blood abnormalities, as well as infections, malignancy, myocardiopathy, and psychiatric disorders. Once we are evaluating a biological product to treat a nail condition, and based on the intrinsic characteristic of side effects that are generally observed in the class of biological products, we believe that these clinical conditions do not warrant the risk of generating or aggravating any of these clinical conditions, based on the following data:

- Liver function test elevations have been reported with the use of tumor necrosis factor inhibitors (TNF-I) in patients with rheumatoid arthritis receiving adalimumab, etanercept, or infliximab (22). The overall incidence of liver function test elevations >1x ULN with TNF-I use was uncommon, and abnormalities >2x ULN were rarely observed. Significant differences were most consistently observed with infliximab, less commonly with adalimumab, and were not observed with etanercept compared with comparator disease-modifying antirheumatic agents (DMARDs) (23).
- It is already described in the literature cases of vasculitis developed in association with the use of tumor necrosis factor-α (TNF-α) inhibitors. Although cutaneous small-vessel vasculitis was the most common finding, but systemic vasculitis, including peripheral nerve and renal vasculitis, was also frequently observed. (23, 24)
- Cases of drug-induced hemolytic anemia after treatment with infliximab and adalimumab for treating ulcerative colitis and psoriasis, respectively, were described. (25, 26)
- An observational cohort study was conducted using medical and outpatient pharmacy claims from 2 large US health insurance claims databases from January 1, 2003, through September 30, 2015. The databases included 31,595 patients in the Optum Clinformatics Data Mart and 76,112 patients in Truven MarketScan who were new users of acitretin, adalimumab, apremilast, etanercept, infliximab, methotrexate, and ustekinumab. The pooled PS-matched analysis yielded a decreased rate of overall serious infection in users of apremilast (hazard ratio [HR], 0.50; 95% CI, 0.26-0.94), etanercept (HR, 0.75; 95% CI, 0.61-0.93), and ustekinumab (HR, 0.65; 95% CI, 0.47-0.89) compared with methotrexate. We did not find a different rate of overall serious infection among users of acitretin, adalimumab, and infliximab compared with methotrexate. (27)

- There is little research on the use of biologic treatment in psoriasis patients with a history of established malignancy (28). The existing evidence is not in all cases sufficient in order to provide adequate insight into the management of these complex situations (29); however, positive associations between cutaneous squamous cell carcinomas and certain therapies have been found, and there is conflicting evidence regarding the risk of lymphoma and melanoma. Further studies are needed to determine the long-term safety of newer psoriasis treatments (interleukin [IL]-12/23, IL-17, Janus kinase 1/3, and phosphodiesterase-4 inhibitors), specifically their safety in patients with a history of cancer (30).
- In a Korean, nationwide population-based prospective cohort study with a 15-year observational period. During the baseline period (1997-2000), total 1,773,786 Korean subjects who received health insurance from the National Health Insurance System were enrolled, and 5,788 subjects were defined as a psoriasis group. The number of newonset malignancies was collected during the observational period (2001-2015). Patients with psoriasis had a higher adjusted hazard ratio (aHR) for the development of overall malignancy (aHR 1.08, 95% confidence interval [CI] 1.00-1.18) and gastric cancer (aHR 1.31, 95% CI 1.08-1.58) compared to controls. The risks of non-Hodgkin lymphoma and non-melanoma skin cancer were significantly increased only in patients with psoriasis who received systemic treatments (aHR 2.86, 95% CI 1.07-7.61 and aHR 3.93, 95% CI 1.47-10.47, respectively) (31).
- Severe dilated cardiomyopathy induced by adalimumab and ustekinumab (32). Cardiac tamponade related to infliximab induction therapy was described, likely due to a type 3 hypersensitivity immune-complex reaction resulting in a reactive pericardial effusion (33). However, major cardiovascular events with tildrakizumab is considered low (34).
- Patients with psoriasis have an increased risk of psychiatric comorbidities, suicidal ideation, and long-term course of the disease compared with patients who have other dermatological conditions (35, 36). However, concerns have been raised regarding the potential link between interleukin-17R blockade in the treatment of psoriasis and suicide, even if the current literature provides no evidence to support this association (36).

This study is planned to be a multicenter, randomized, double-blind, placebo-controlled study to evaluate the efficacy and safety of the approved dose of tildrakizumab (100 mg by SC injection) in the treatment of moderate to severe nail psoriasis.

2.3 Benefit/Risk Assessment

Details about specific benefits and risks for subjects in this clinical study can be found in the Investigator Brochure (IB) and the informed consent form (ICF).

Given that efficacy benefits were reported in the completed Phase 2b study (Protocol P05495) and Phase 3 studies (P010 and P011) in plaque psoriasis, there is an expectation that subjects

treated with tildrakizumab will demonstrate improvement in nail psoriasis disease activity and Quality of life at Week 28. The study design allows early identification of subjects who have worsening of psoriasis at Week 16 and Week 28 and will be discontinued from treatment.

The study has also been designed to minimize potential risks to subjects; all subjects will undergo screening procedures aimed at reducing the likelihood and impact of any such risks. In addition, regular safety monitoring during the treatment period for all subjects will ensure that any unanticipated effects of study participation are identified promptly and managed appropriately. Given the long half-life (T_{1/2}) of tildrakizumab at doses previously studied, subjects will continue to be monitored throughout a 20-week wash-out period following the EoT visit, during which no active study treatment will be administered.

This study will be performed in compliance with the protocol, the International Council for Harmonisation (ICH), Good Clinical Practice (GCP), and applicable regulatory requirements.

3.0 OBJECTIVES AND ENDPOINTS

Table 2: Study Objectives and Endpoints

OBJECTIVES	ENDPOINTS
PRIMARY EFFICACY OBJECTIVE	PRIMARY EFFICACY ENDPOINT
To assess the efficacy of tildrakizumab in subjects with moderate to severe nail psoriasis, as measured by the proportion of subjects who achieve at least a 75% improvement from baseline in total-modified Nail Psoriasis Severity Index (mNAPSI) at Week 28.	The proportion of subjects who achieve at least a 75% improvement from baseline in total-mNAPSI at Week 28.
SECONDARY OBJECTIVES	SECONDARY ENDPOINTS
To assess the efficacy of tildrakizumab in the treatment of moderate to severe nail psoriasis compared with placebo as measured by ViSENPsO at Week 28. (Key secondary objective)	• The proportion of subjects with a score of "0 - normal" or "1 - minimal nail psoriasis" and at least a 2-point decrease from baseline at Week 28 as measured by the ViSENPsO. (Key secondary endpoint)
To assess the effect of tildrakizumab on nail pain compared with placebo as measured by nail pain numeric rating scale (NRS) score at Week 28.	• The proportion of subjects with at least 3 point decrease from baseline in Nail Pain NRS score at Week 28 in subjects with baseline nail pain NRS score of ≥ 3*
• To assess the effect of tildrakizumab on nail pain compared with placebo as measured by nail pain numeric rating scale (NRS) score at Week 28.	Change in patient-reported nail pain NRS score from Baseline at Week 28.
To assess the efficacy of tildrakizumab in the treatment of moderate to severe nail psoriasis compared with placebo as measured by mNAPSI, NAPSI, and ViSENPsO at Week 28.	 The proportion of subjects achieving total-fingernail mNAPSI 90, mNAPSI 100, NAPSI 75, NAPSI 90, and NAPSI 100 at Week 28. Change in total-fingernail mNAPSI score from baseline at Week 28. Change in total-fingernail NAPSI score from baseline at Week 28.
To assess the efficacy of tildrakizumab in the treatment of plaque psoriasis compared with placebo, as measured by Psoriasis Area and Severity Index (PASI), Physician's Global Assessment-Skin (PGA-S) score and body surface area (BSA) involvement at Week 28.	 The proportion of subjects achieving PASI 75, PASI 90, and PASI 100 at Week 28. The proportion of subjects achieving a PGA-S score of "clear" or "almost clear" with at least 2-point reduction from baseline to Week 28. Percentage change in total BSA involvement from baseline to Week 28.

OBJECTIVES	ENDPOINTS
To assess the effect of tildrakizumab on nail pain compared with placebo as measured by nail pain NRS score improvement at Week 28.	• The proportion of subjects with at least a 30% decrease in Nail Pain NRS score from Baseline at Week 28 in subjects with a baseline nail pain NRS score of > 3*.

EVELODATODY OD JECTIVES	EVDLODATODY ENDDOINTS
 EXPLORATORY OBJECTIVES To assess the effect of tildrakizumab over time 	• Change from Baseline in mNAPSI, NAPSI,
at measured time points through Week 52 as measured by mNAPSI, NAPSI, Nail Pain NRS, BSA, PGA-S, static Physician's Global	Nail Pain NRS, BSA, PGA-S, sPGA, PASI,
Assessment (s-PGA), PASI, To assess the effect of tildrakizumab on Quality of Life (QoL) as measured by: Dermatology Life Quality Index (DLQI) and Nail Assessment in Psoriasis and Psoriatic Arthritis QoL (NAPPA- QoL).	Change from Baseline in DLQI score (total and 6 domain scores) and NAPPA-QoL score at measured time points through Week 52.
 To assess the effect of tildrakizumab measured by using anchor scales: Clinician Global Impression of Change (CGIC) Clinician Global Impression of Severity (CGIS) Patient Global Impression of Change (PGIC). Patient Global Impression of Severity (PGIS). Patient Global Impression of Severity for pain (PGIS-P). Patient Global Impression of Change for pain (PGIC-P). 	Change from Baseline in CGIC, CGIS, PGIC, PGIC-P, PGIS, and PGIS-P at measured time points through Week 52.
SAFETY OBJECTIVE	SAFETY ENDPOINT
To assess the safety and tolerability of tildrakizumab in subjects with moderate to severe nail psoriasis over 52 weeks.	 The percentage of subjects with incidence, seriousness, and severity of all adverse events. The percentage of subjects with severe infections defined as any infection meeting the regulatory definition of a serious adverse event (SAE), or any infection requiring intravenous (IV) antibiotics, whether or not reported as a serious event as per the regulatory definition. The percentage of subjects with malignancies (excluding carcinoma in situ of the cervix). The percentage of subjects with non-melanoma skin cancer.

The percentage of subjects with melanoma
skin cancer.
The percentage of subjects with MACE.
The percentage of subjects with study
treatment-related hypersensitivity reactions
(e.g., anaphylaxis, urticaria, angioedema,
etc.).
The percentage of subjects with injection
site reactions (e.g. pain, erythema, edema
etc.).

4.0 STUDY DESIGN

4.1 Overall Design

This is a multicenter, randomized, double-blind, placebo-controlled study to assess the efficacy and safety of tildrakizumab in the treatment of moderate to severe psoriasis of the nails. The study will be conducted in up to approximately 35 study centers globally. The study duration per subject will be approximately 18 to 19 months, including a treatment duration of 52 weeks, and the total study duration will be approximately 3 years. The study design is presented in Figure 1.

Approximately 96 eligible subjects (approximately 48 per arm) with moderate to severe plaque psoriasis and concomitant moderate to severe nail psoriasis will be randomized into the study. Eligible subjects will be randomized to one of the 2 arms in a 1:1 ratio: Arm A: Tildrakizumab 100 mg, SC (n = 48) and Arm B: Placebo, SC (n = 48). The number of subjects with prior use of TNF-alpha inhibitors will be capped at 40%, and the analysis will be stratified based on prior use of these biologics. The randomization (1:1) to tildrakizumab and placebo will be stratified by 2 factors: prior use of TNF-alpha inhibitors (Yes/No) and Baseline body weight (\leq 90 kg or \geq 90 kg).

In a clinical trial with moderate-to-severe-plaque-psoriasis subjects, guselkumab was compared to adalimumab (VOYAGE 1, NCT02207231). One of the endpoints was nail disease. In that American population, about 20.9% of the subjects had experienced the use of biologic agents before joining the trial (37). In another trial, a 32-week study of secukinumab in subjects with nail psoriasis, performed in Germany, Australia, the Czech Republic, the USA, China, and Switzerland, 23.3% of the subjects had had previous exposure to a biological systemic psoriasis therapy (38). Based on these two recent manuscripts, the experience of the prior use of biological products in psoriasis ranges between 20% through 23.3%. To avoid excessive variability among the clinical sites, which could represent an issue and generate data not compatible with the population at large, it was decided to assume a conservative cap at 40% for this study.

The study will comprise 3 parts:

4.1.1 PART 1: Double-blind Placebo-controlled (Day 1 to Week 28)

After a Screening Period of up to 28 days and on Day 1, all eligible subjects will be randomized

1:1 to receive either tildrakizumab 100 mg or placebo administered by SC injection on Week 0 (Day 1), Week 4, and Week 16. Subjects should receive the first dose of study treatment within 24 hours of randomization. The treatment period for the double-blind, placebo-controlled part of the study is 28 weeks.

Early Escape: At Week 16, subjects who experience significant worsening of plaque psoriasis (defined as an increase in s-PGA by at least 2 from the baseline measurement) will be eligible for an early escape. (Appendix 20) Subjects selected for early escape by the Principal Investigator at Week 16 will have study medication discontinued and will complete the End of Treatment visit

assessment, followed by the observational safety follow-up period. Subjects entering early escape may be replaced so as to meet the planned evaluable sample size goal for the primary endpoint analysis.

An interim analysis may be performed that could include an unblinded sample size re-estimation (SSRE). The sample size of the study could be increased as a result of this SSRE. In the event of an increase in sample size, the total sample size of the study will not exceed a total of approximately 282 randomized subjects.

4.1.2 PART 2: Double-blind Active Treatment Extension (Week 28 to Week 52)

At Week 28, subjects initially randomized to placebo will be switched over to receive tildrakizumab 100 mg at Weeks 28, 32, and 44. Subjects initially randomized to tildrakizumab 100 mg will continue to receive tildrakizumab at Weeks 28, 40, and 52. In order to maintain the blind, subjects in both treatment arms will receive matching placebo injections at specified time points as described in the SoA.

Subjects who experience significant worsening of plaque psoriasis at Week 28 (defined as an increase in s-PGA by, at least 2 from the baseline measurement) will be discontinued from treatment. Subjects who do not fulfill this criterion at Week 28 will continue to receive tildrakizumab in Part 2, as described above.

4.1.3 PART 3: Observational Safety Follow-up (Week 52 to Week 72)

After Week 52 (or early termination of study treatment prior to Week 52), the study treatment should be stopped and all subjects, including those who terminated early from Part 1 and, 2 will enter the 20-week Observational Safety Follow-up period to monitor safety and tolerability for 20 weeks following the last dose of study treatment. During the follow-up period, subjects should continue on study-approved concomitant medications only, however, may be placed on appropriate therapies for safety concerns or significant worsening of psoriasis based on the judgment of the Investigator. The subjects will not receive study treatment during the follow-up period.

The study may have a primary analysis, which will be performed when the last subject has completed the Week 28 visit, and a final analysis to be performed when the last subject has completed the study.

Subjects who withdraw from the study will undergo the assessment that corresponds to the last assessment of the study part from which they are leaving. Subjects discontinued from study treatment at any time (apart from the withdrawal of informed consent) will complete the EoT (Week 52) assessment approximately 4 weeks after the last dose of study treatment and enter the 20-week observational safety follow-up. Subjects who withdraw from the study during Part 3 will undergo the Week 72 (End of Study [EoS]) assessments approximately 4 weeks after their last visit.

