6.5 Concomitant Therapy

Any medication or vaccine (including over-the-counter [OTC] or prescription medicines, vitamins, and/or herbal supplements) that the subject is receiving at the time of enrollment or receives during the study must be recorded on the eCRF along with:

- Reason for use.
- Dates of administration, including start and end dates.
- Dosage information, including dose and frequency.

In addition, all prior medications used to treat the disease conditions and any other medications taken within 6 months prior to enrollment must be recorded in the eCRF.

The Medical Monitor should be contacted if there are any questions regarding concomitant or prior therapy.

A list of excluded medications/therapy is provided in Table 4.

Other concomitant medication may be considered on a case-by-case basis by the Investigator in consultation with the Medical Monitor if required.

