8.3.1 Time Period and Frequency for Collecting AE and SAE Information

Any relevant observations made before the end of the Screening and Baseline visit (prior to the first dose of study treatment) are to be recorded on the AE eCRF, but will not be considered TEAEs and will be reported separately from TEAEs. Any relevant observations made after the first dose of study treatment will be recorded as an AE in the subject's AE eCRF (see Section 1.3).

In view of the long half-life of tildrakizumab at doses previously studied, subjects will continue to be monitored throughout the 20-week Observational Safety Follow-up period following the EoT (Week 52) visit. For the purposes of this study, any detrimental change in the subject's condition after the first dose of study treatment and up to the completion of the EoS visit should be considered an AE. For those subjects who may withdraw during the Observational Safety Follow-up period or wash-out period, at least 2 attempts should be made to collect the AEs.

A hospitalization planned by the subject prior to signing the ICF is considered a therapeutic intervention and not the result of a new SAE and should be recorded as medical history. If the planned hospitalization or procedure is executed as planned, the record in the subject's medical history is considered complete. However, if the event/condition worsens during the study, it must be reported as an AE.

Medical occurrences that begin before the start of study treatment but after obtaining informed consent will be recorded on the AE section of the eCRF however will not be considered as TEAEs.

All SAEs will be recorded and reported to the CRO within 24 hours, as indicated in Appendix 3. The Investigator will submit any updated SAE data to the CRO within 24 hours of it being available. The Investigator is responsible for informing the Ethics Committee of the SAE as per local requirements. All AEs/SAEs have to be reported to the Sponsor, whether or not considered causally related to the study treatment or to the study procedures.

Investigators are not obligated to actively seek AE or SAE after conclusion of the study participation. However, if the Investigator learns of any SAE, including death, at any time after a subject has been discharged from the study, and he/she considers the event to be reasonably related to the study treatment or study participation, the Investigator must promptly notify the CRO.

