After Week 52 (or early termination of study treatment prior to Week 52), the study treatment should be stopped and all subjects, including those who terminated early from Part 1 and 2 will enter the 20-week Observational Safety Follow-up period to monitor safety and tolerability for 20 weeks following the last dose of study treatment. During the follow-up period, subjects should continue on study-approved concomitant medications only, however, may be placed on appropriate therapies for safety concerns or significant worsening of

| Effective Date: 10-AUG-2020 | Page 10 of 61 |
|-----------------------------|---------------|

psoriasis based on the judgment of the Investigator. The subjects will not receive study treatment during the follow-up period.

Subjects who withdraw from the study will undergo the assessment that corresponds to the last assessment of the study part from which they are leaving. Subjects discontinued from study treatment at any time (apart from withdrawal of informed consent) will complete the EoT (Week 52) assessment approximately 4 weeks after the last dose of study treatment and enter the 20-week Observational Safety Follow-up. Subjects who withdraw from the study during Part 3 will undergo the Week 72 (End of Study [EoS]) assessments approximately 4 weeks after their last visit.

All assessments of safety in PART 3 are scheduled to happen after the date of injection at Week 52. The analysis of efficacy and safety endpoints for PART 3 will follow the analysis visit window and definitions as specified in the sections below.

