10.1 Adverse Events

The incidence of treatment-emergent AEs (TEAE) will be summarized and tabulated by treatment group, MedDRA (Version 24.0 or higher) System Organ Class (SOC) and Preferred Term (PT). A TEAE is defined as an AE that first occurred or worsened in severity after the first administration of study treatment.

AEs that cannot be definitely determined as occurring prior to first study drug administration will be counted as TEAEs unless either the partial start date or a partial or complete end date indicates the AE as occurring prior to treatment. Partial dates entered in the AE form will be imputed for the purposes of determining whether the record is a treatment emergent adverse event based on the following:

- AE onset dates with missing day and non-missing month will be assumed to occur on the first day of the non-missing month, except for AEs occurring in the month and year of first dosing of study drug, in which case the date will be imputed using the date of first dosing of study drug.
- AE onset dates with missing day and month will be assumed to occur on the first day
 of the non-missing year (i.e., January 1), except for AEs occurring in the year of first
 dosing of the study drug, in which case the date will be imputed using the date of the
 first dosing of study drug.
- Partial or missing AE resolution dates will not be imputed.

Several occurrences of the same AE in one subject will be counted once at the worst severity grade. If severity is missing, the event will be classified as of unknown severity for analysis and summarization.

The relationship of each AE to the study drug will be grouped as related (definitely, probably, possibly related) or unrelated (unlikely to be related, unrelated). Several occurrences of the same AE in one subject will be counted once and the one with the closest relationship to study medication will be counted. If an AE is missing the relationship to study medication, the event will be assumed to be related to study drug for analysis and summarization.

AEs will be further categorized by Study Part (1, 2, 3) as follows:

- Part 1 (Day 1 to Week 28): includes all AEs that first occurred or worsened in severity after the first study medication administration, but do not start after the Week 28 study medication administration.
- Part 2 and 3 (Week 28 and beyond): includes all AEs that first occurred or worsened in severity after the Week 28 injection. These will be performed for the final analyses.

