| Effective Date: 10-AUG-2020 | Page 41 of 61 |
|-----------------------------|---------------|

Non-TEAEs will be listed only and will not be included for analysis and summarization.

All AEs will be presented in a by-treatment and by-subject listing for Part 1, detailing the verbatim term, SOC, PT, injection site reaction or not, related to study indication or not, start date, stop date, time since most recent dose of IP, severity, outcome, relationship to study drug, action taken regarding study drug, other action taken, seriousness and criteria for seriousness. Serious AEs (SAEs) and TEAEs leading to study medication discontinuation, AEs of Special Interest (AESI), and events of clinical interest (ECI) will also be presented in separate listings.

An AE profile for the SAF will be provided for Part 1, Parts 2 and 3, and overall, which summarizes the subject incidence, by treatment received for the following information:

- Any TEAEs;
- Drug-related TEAEs;
- Any TEAEs with an outcome of death;
- Treatment-emergent SAEs;
- Drug-related treatment-emergent SAEs;
- TEAEs leading to discontinuation of study medication;
- Drug-related TEAEs leading to discontinuation of study medication;
- Any AEs of special interest, including:
 - Injection site reactions
 - Severe infections
 - o Malignancies (excluding carcinoma in situ of the cervix).
 - Non-melanoma skin cancer
 - Melanoma skin cancer
 - Major Adverse Cardiovascular Events (MACE)
 - Study treatment-related hypersensitivity reactions (e.g., anaphylaxis, urticaria, angioedema, etc.).

| Effective Date: 10-AUG-2020 | Page 42 of 61 |
|-----------------------------|---------------|

Study treatment-related hypersensitivity reactions will be identified based on Sponsor review of treatment-blinded listings of AE preferred terms prior to declaration of the IA DB freeze.

The number and percentage of subjects with TEAEs will be summarized for each treatment arm and/or in total by SOC and PT. Drug-related TEAEs, TEAEs leading to discontinuation of study drug, drug-related TEAEs leading to discontinuation of study drug, treatment-emergent SAEs, and drug-related treatment-emergent SAEs, AESI and ECI will be summarized in the same manner. For these summaries, subjects with multiple AEs will be counted only once per SOC and PT.

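### Adverse events that begin on another psoriasis therapy during follow-up are counted in the study arm, and SAP 10.1 describes no table that separates them

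*Protocol*

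**What the plan says.** **Therapy in follow-up.** Protocol 4.1.3 puts all subjects, including those who stop early in Part 1 or Part 2, into a 20-week observation period. The default is to stay on medication the study already permits, but subjects "may be placed on appropriate therapies for safety concerns or significant worsening of psoriasis based on the judgment of the Investigator". No drug class is ruled out for that period. The exclusions in Protocol 6.8 concern use together with study treatment, and Protocol 6.7 asks for ordinary psoriasis care. SAP 2.1 repeats the permission.

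**Collection.** Under Protocol 8.3.1, a deterioration "after the first dose of study treatment and up to the completion of the EoS visit should be considered an AE". Follow-up is therefore inside the collection window.

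**Definition and tabulation.** SAP 10.1 states: "A TEAE is defined as an AE that first occurred or worsened in severity after the first administration of study treatment". The later reporting period is "Part 2 and 3 (Week 28 and beyond): includes all AEs that first occurred or worsened in severity after the Week 28 injection". Part 1 takes events from the first dose that do not start after the Week 28 administration. The AE profile "will be provided for Part 1, Parts 2 and 3, and overall, which summarizes the subject incidence, by treatment received", with TEAE, SAE and AESI rows. The only further group, in SAP 10, is former placebo subjects who move to tildrakizumab.

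**Medication dates.** Protocol 6.5 requires "Dates of administration, including start and end dates" for each concomitant drug. SAP 7.3 summarises and lists these drugs but does not relate them to AE onset.

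**The concern.** A reader of the safety tables needs to tell events on tildrakizumab from events on a drug started afterwards. The plan collects the dates that would allow this but sets no rule for using them. An injection site reaction to a replacement injectable, or a severe infection while taking it, enters the AESI rows of the arm the subject came from.

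Two displays are affected. The first is the pooled table for Parts 2 and 3. The safety objective (Protocol 3.0, SAP 2.2.4) covers 52 weeks, yet SAP 10.1 describes no AE table that stops at Week 52 or shows Part 3 alone. The second is the Part 1 table, the only placebo-controlled comparison, which subjects who leave before Week 28 can affect. With this many subjects per arm, one event can visibly change a sparse row.

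**Working it through.** **1. Denominator.** The plan's own figure reproduces. Protocol 9.2 assumes 35% versus 10%, two-sided alpha 0.05, 80% power and a pooled Z-test.

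- Mean proportion = (0.35 + 0.10)/2 = 0.225.
- n = [1.96 × √(2 × 0.225 × 0.775) + 0.8416 × √(0.35 × 0.65 + 0.10 × 0.90)]² / 0.25² = (1.157 + 0.474)² / 0.0625 = 42.6, so 43 per arm.
- With 10% dropout: 43/0.90 = 47.8, so 48 per arm.

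The point uses only the 48. It does not depend on the response rates.

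**2. The passages side by side.**

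| Step | Source | Limit at start of another therapy? |
|---|---|---|
| Other therapy permitted in follow-up | Protocol 4.1.3, SAP 2.1 | – |
| AEs collected to the end-of-study visit | Protocol 8.3.1 | No |
| TEAE defined by onset after first dose | SAP 10.1 | No |
| Tabulated by treatment received | SAP 10.1 | No |
| Start and end dates of other drugs recorded | Protocol 6.5 | Available, not used |

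**3. Share of the pooled period that is follow-up (nominal schedule).** Parts 2 and 3 run from Week 28 to Week 72, which is 44 weeks. Follow-up is Weeks 52 to 72, which is 20 weeks. 20/44 = 45%; of the whole study, 20/72 = 28%. This is time without further dosing, not drug-free time: Arm A receives an active dose at Week 52 and Arm B's last active dose is at Week 44 (Protocol 6.0).

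**4. Early leavers and Part 1.** A subject who leaves before Week 28 has no Week 28 administration, so the Part 1 rule in SAP 10.1 sets no date for that subject beyond the label of Day 1 to Week 28. Two other boundaries exist, and SAP 10.1 uses neither:

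- Protocol 9.5 limits the Week 28 analysis to Day 210 for subjects without that injection. The Week 16 visit is nominally Day 16 × 7 + 1 = 113, so up to 210 − 113 = 97 days of follow-up after a Week 16 exit could still fall in Part 1.
- SAP 3.3 gives early terminators their own Part 3 start, tied to the last assessment and 28 days after the last injection.

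**5. Size.**

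- One affected subject: 1/48 = 2.1 percentage points of a row, and only if that subject is not already counted in it. At the re-estimation ceiling of 282 subjects (Protocol 9.5), 282/2 = 141 per arm and 1/141 = 0.7 points.
- The documents give no switching rate. As an assumed range, suppose 2 to 10 of 48 subjects per arm start another therapy and 10% to 30% of those have an event on it. The contribution is 2 × 0.10/48 = 0.4 points to 10 × 0.30/48 = 6.3 points. Within these assumptions this is an upper limit, because some subjects will already be counted for an earlier event.

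**The case against.** **Attribution through follow-up is deliberate.** Protocol 2.3 and 8.3.1 justify the follow-up by the drug's long half-life. Counting later events under the study arm is a conservative safety convention. This stands, and it is why the all-TEAE tables should remain the main display. It does not explain the absence of any supplementary separation.

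**Causality assessment already deals with it.** Protocol Appendix 3 has the investigator weigh concomitant therapy, and SAP 10.1 tabulates drug-related events separately. This helps the drug-related rows and the hypersensitivity row, which is restricted to treatment-related reactions. The all-TEAE, SAE, injection site reaction, severe infection, malignancy and MACE counts do not change.

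**Listings allow reconstruction.** They do, in part: AE and medication dates are recorded. A split chosen after the treatment codes are known is weaker than one fixed beforehand.

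**A table may be planned elsewhere.** The text of SAP Sections 8, 12 and 16 is not readable in the public copy, so a planned display cannot be excluded. SAP 10.1 itself reads as complete on this point.

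**A stronger reading.** A reader might infer that placebo subjects who switch would inflate the placebo column and hide a tildrakizumab excess. The documents do not support that. From Week 28 both arms receive tildrakizumab, so Parts 2 and 3 have no placebo comparator, and SAP 10 identifies former placebo subjects separately. The route needs placebo subjects who stop before Week 28. Early escape at Week 16 requires a rise of at least 2 on s-PGA, with entry at 3 or more and a maximum of 5, so only a subject going from exactly 3 to 5 qualifies. Other early discontinuations are possible under Protocol 7.1, but no rates are given. Nor do the documents say that relapse treatment is expected; Protocol 4.1.3 permits it as an exception.

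**Conclusion.** The gap is real and limited. On the readable text, events within the follow-up window that begin on a replacement drug are counted in the study arm's all-TEAE and SAE rows and in its AESI rows other than treatment-related hypersensitivity. For early leavers they can also fall in the placebo-controlled Part 1 table. It would go too far to say that every later event is counted: Protocol Appendix 3 limits reporting after 20 weeks from the last dose to events judged related.

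The total effect cannot be estimated from the documents. What can be stated is 2.1 points per affected subject at 48 per arm, conditional on no earlier event in that row. Safety is analysed descriptively, so no test or error rate is affected. This is a cheap improvement worth making before the Week 28 database freeze, not a flaw that undermines the trial.

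**What to change.** In SAP 10.1:

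1. Keep the all-TEAE tables as the main display.
2. Derive a flag for AEs with onset on or after the start date of any other systemic, biologic or phototherapy treatment for psoriasis, using the concomitant treatment records.
3. Pre-specify supplementary AE profile, AESI and SOC/PT tables with and without flagged events.
4. Show Part 3 separately from Part 2.
5. State in the AE period definition where Part 1 ends for subjects with no Week 28 administration. Either the SAP 3.3 Part 3 start or the Day 210 limit of Protocol 9.5 would serve, but they give different cut-offs, so name one.

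The cost is one derived variable and a few repeat tables, with no new data collection. The drawback is that a late tildrakizumab effect appearing after a switch would be flagged and leave the cut-off tables, and the switch itself may depend on how the subject is doing. Both sets should therefore be reported, and conclusions should not rest on the cut-off tables alone.
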